13. LIMITATIONS AND BIASES

The VR-CP retrospectively enrolls patients who underwent coronary angiography documenting at least one mild to intermediate coronary lesion assessed by coronary physiology tests (FFR or angiography-derived FFR). The retrospective enrolment may not be fully representative of the general population or could be influenced by prior clinical decisions, thus introducing selection bias. To mitigate this issue, consecutive patients are enrolled, ensuring a more representative and generalizable sample. This approach minimizes the influence of selection bias, investigator bias, and temporal bias, improving the logistical simplicity and scientific rigor of the study. Our goal is to ensure that the sample reflects the typical patient population encountered in routine clinical practice.

Another limitation is that historical data might reflect medical practices or diagnostic techniques that are no longer routinely used or have evolved over time, limiting the generalizability of the results.

An independent Clinical Event Committee (CEC) evaluates all endpoints. The CEC members and management team are fully blinded to patients' identifying information. The CEC adjudicates events based on predefined definitions. Additional measures to prevent or minimize bias include the use of objective criteria for endpoint classification. Finally, unlike prospective randomized studies, this retrospective study does not include randomization, which may lead to uneven distribution of risk factors.

14. ADVERSE EVENTS

Definitions

Adverse Events (AEs) / Serious Adverse Events (SAEs) / Incidents:

Any undesirable medical occurrence in a clinical study during which a patient receives the study treatment, and which does not necessarily have a causal relationship with such treatment or with any device malfunction. An AE can therefore be an unintended and accidental manifestation, represented by a sign (including an abnormal laboratory result), a symptom, or a disease, whose onset is temporally associated with the study treatment or with any device malfunction, whether related or unrelated to the study treatment.

Serious Adverse Event (SAE):

Any undesirable medical event or device malfunction that results in one or more of the following outcomes:

- Death
- Life-threatening condition
- Hospitalization or prolongation of existing hospitalization
- Persistent or significant disability/incapacity
- Congenital anomaly/birth defect
- Medically significant event or one that requires intervention to prevent any of the above outcomes. If an event meeting the SAE definition occurs after signing the informed consent form but before patient inclusion, it should not be reported as an SAE. Such an event may be reported in the appropriate section of the Case Report Form (CRF).

For medical devices and active implantable medical devices, an incident is defined as:

- a) Any malfunction or deterioration in the characteristics or performance of a medical device/active implantable medical device, as well as any inadequacy in labeling or

instructions for use, which may have caused or contributed to death or serious deterioration in the health condition of a patient or user;

b) Any technical or medical reason related to the characteristics or performance of a medical device/active implantable medical device that leads to the systematic recall of devices of the same type by the manufacturer for reasons described in point (a). (Decree Legislative 24 February 1997, n. 46 – Implementation of Directive 93/42/EEC concerning medical devices, amended by D. Lgs. 25.01.2010, n. 37).

Monitoring of Adverse Events, Serious Adverse Events, and Incidents

As established by the Investigator, patients who experience Adverse Events (AEs), Serious Adverse Events (SAEs), or Incidents will be evaluated using relevant clinical assessments and laboratory analyses. Any actions taken and the outcomes of follow-up must be recorded in the patient's original documentation and in the appropriate sections of the Case Report Form (CRF).

To obtain evidence of adverse events throughout the entire case series, the patient will be interviewed and/or examined by the Investigator or an authorized delegate. Questions asked to patients regarding the possible occurrence of adverse events should be as non-specific as possible. However, since the center is responsible for conducting follow-up for all cases of AEs, specific questions regarding previously reported AEs, SAEs, and Incidents must be included concerning their resolution or continuation.

For treatment-related AEs/SAEs/Incidents, relevant clinical evaluations and laboratory analyses will be repeated until the event is fully resolved, stabilized, or its cause explained.

SAEs not related to treatment that remain unresolved at the completion of the case series must be followed for a maximum period of one month after the case series completion.

Reporting of Adverse Events, Serious Adverse Events, and Incidents

The reporting of an incident (whose definition is included within that of “serious adverse effect” used in clinical trials – see technical standard UNI EN ISO 14155-11) involving medical devices under post-marketing investigation must be carried out similarly to the reporting for medical devices used in routine clinical practice, through the completion of the Ministry’s form for MD/IVD (Medical Devices/Active Implantable Medical Devices) — which requires indicating the study code number — or the form related to IVDs (In Vitro Diagnostics). A copy of the report must also be sent to the relevant Ethics Committee.

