OCT: optical coherence tomography

PCI: percutaneous coronary intervention

SAE: serious adverse event

SAQ: Seattle angina questionnaire

TCFA: thin cap fibroatheroma

TVR: target vessel revascularization

VOCE: vessel-oriented cardiac adverse events

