1. SYNOPSIS

Study title	Verona coronary physiology interventional registry (VR-CP)
Protocol version	V1
Date	March, 1 st 2025
Study sponsor	Azienda Ospedaliera Universitaria Integrata di Verona
Study principal investigator	[name] MD PhD
Patient population	The observational Verona Coronary Physiology Interventional Registry (VR-CP) study enrolls patients with suspected coronary artery disease who underwent coronary angiography with functional assessment (coronary physiology).
Primary objective	The primary objective is to assess the functional characteristics of coronary lesions documented during coronary angiography and correlate them with the risk of cardiovascular events during follow-up.
Secondary objective	
- To examine the prognostic value of physiological parameters (FFR and angiography-derived FFR).- To analyze the clinical, demographic, and angiographic characteristics of patients with coronary lesions assessed by coronary physiology parameters, in order to identify high-risk subgroups.- To correlate coronary physiology values with angina symptoms.- To compare invasive FFR with angiography-derived FFR.- To compare clinical outcomes between patients managed conservatively and those undergoing invasive interventions.
Study design	The VR-CP study is a single-center observational study enrolling consecutive patients with coronary stenoses documented during coronary angiography and functionally assessed with coronary physiology (fractional flow reserve [FFR] or angiography-derived FFR) performed for suspected ischemic heart disease. Follow-up is conducted, after obtaining informed consent, through telephone contact and/or outpatient visits. Adverse events are adjudicated by an independent clinical events committee, blinded to clinical data.
Data source	The selection of eligible patients is extracted from registries and the analysis of coronary angiographic studies performed from January 2010 to December 2024.
Sample size	Enrollment will include approximately 1,000 patients evaluated with FFR or angiography-derived FFR. This sample size will allow for subgroup analyses stratifying lesions by functional severity based on FFR values.
Inclusion criteria	
- Coronary angiography with functional assessment by FFR or angiography-derived FFR (index procedure)- Provision of written informed consent- Age \geq18 years old at the time of the index procedure

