Exclusion Criteria	
- Inability to provide informed consent to participate in the study
Informed Consent	Patients identified as eligible for the protocol will be invited to provide informed consent for participation in the retrospective study through contact by telephone, e-mail, mail, or during an outpatient visit.
Study Procedures	Once eligibility for the protocol is confirmed, informed consent is requested and obtained. After enrolment, the angiographic images from the index coronary angiography are analysed by the investigators. Long-term follow-up is performed by monitoring the clinical status and recording major adverse cardiac events through review of medical records, outpatient visits, or telephone contacts.
Primary Endpoint	Composite of vessel-oriented composite endpoint (VOCE), including target vessel revascularization (TVR), target vessel-related myocardial infarction (MI), and cardiovascular death.
Secondary Endpoints	
- Individual components of the primary endpoint- Hospitalization for unstable angina- Angina status (Seattle Angina Questionnaire)- Number of prescribed antianginal medications
Study Duration	Patients are retrospectively enrolled from January 2010 to December 2024. Clinical contact (medical records, outpatient visits, telephone communication) is periodically collected recording longitudinal data at 12-month intervals.
Clinical Event Adjudication Committee	The following events are adjudicated by an independent committee blinded to clinical data: TVR, target vessel-related MI, cardiovascular death, and hospitalization for unstable angina.

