3. STUDY DESIGN

The Verona Coronary Physiology Interventional Registry (VR-CP) study is a single-center, single-arm, observational study with blinded event adjudication. VR-CP enrolls patients who underwent coronary angiography for suspected ischemic heart disease, in whom at least one coronary lesion was identified and functionally assessed by coronary physiology testing (fractional flow reserve [FFR] or angiography-derived FFR).

Eligible patients are identified through registry data and review of coronary angiographic studies performed from January 2010 to December 2024. Patients meeting inclusion criteria are invited to provide written informed consent to participate in the observational study. Recruitment may occur through telephone, mail, email, or during outpatient visits. All study data are recorded in an anonymized electronic case report form (eCRF).

The follow-up involves periodic recording of the clinical status and reporting of any adverse events through review of medical records, outpatient visits, or telephone communications, in order to ensure longitudinal data collection at 12-month intervals.

Adverse events are adjudicated by an independent Clinical Event Committee (CEC) blinded to all patient clinical data. Investigators will provide the CEC with anonymized clinical documentation relating to the reported adverse event. The CEC will adjudicate events that are part of the study's primary and secondary endpoints. Event definitions and adjudication rules are established by the

Principal Investigators and recorded in the Adjudication Committee Charter. The adjudication outcomes determined by the CEC will be used for the final statistical analysis.

CEC members will be appointed by the Principal Investigator at the time of study activation. They will be selected among experienced cardiologists with no access to the clinical documentation of enrolled patients.

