8. PLANNED PROCEDURES AND DATA COLLECTION

The VR-CP study is a retrospective observational study enrolling consecutive patients who underwent coronary angiography for suspected ischemic heart disease and were found on angiographic examination to have coronary lesions evaluated using coronary physiology testing (FFR or angiography-derived FFR). These physiology assessments guided the decision to proceed with or defer target vessel revascularization.

Regardless of whether the lesion was treated invasively or managed conservatively, patients' clinical status and any adverse events are periodically recorded.

[figure not shown]
This retrospective follow-up is conducted through the collection of information from medical records, direct contact during outpatient visits, or via telephone communications, in order to ensure longitudinal data collection at 12-month intervals.

Fig. 1
Summary of Activities Performed

Flowchart

Fig.2 Retrospective Observational Study Design

*at the time of index procedure

DATA MANAGEMENT AND PROCEDURES TO ENSURE DATA CONFIDENTIALITY

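### The Section 14 rule that patients be asked about adverse events as non-specifically as possible also covers, as worded, the interviews used to find endpoint events

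*Protocol*

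**What the plan says.** The instruction is in Protocol Section 14, under the monitoring of adverse events: "Questions asked to patients regarding the possible occurrence of adverse events should be as non-specific as possible". The sentence after it makes one exception: "specific questions regarding previously reported AEs, SAEs, and Incidents must be included concerning their resolution or continuation".

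Elsewhere the protocol applies the same term to endpoint events.

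- The Synopsis (Section 1, study design) states: "Adverse events are adjudicated by an independent clinical events committee, blinded to clinical data". Section 3 repeats this and then says that what the committee adjudicates are the events belonging to the primary and secondary endpoints.
- The abbreviations list has "VOCE: vessel-oriented cardiac adverse events", although the Synopsis and Sections 4 and 7 expand VOCE as a composite endpoint.

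On sources, Section 3 describes "reporting of any adverse events through review of medical records, outpatient visits, or telephone communications". The Synopsis (study procedures) has "recording major adverse cardiac events through review of medical records, outpatient visits, or telephone contacts", and Section 8 says "This retrospective follow-up is conducted through the collection of information from medical records, direct contact during outpatient visits, or via telephone communications". On what reaches the committee, Section 3 says: "Investigators will provide the CEC with anonymized clinical documentation relating to the reported adverse event".

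**The concern.** Open, non-leading questions are normal when collecting unexpected safety events. They are a poor tool for finding a short, predefined list of dated events. A patient asked in general terms how things have been may not mention an admission or a PCI at another hospital some years earlier. A patient asked directly about it is more likely to.

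Three endpoint events can be found by asking the patient: target-vessel infarction and target vessel revascularization (both in the primary composite) and hospitalization for unstable angina (secondary). If one of them is not mentioned and is not in the centre's own records, no documentation is assembled and the committee never sees it. Blinded adjudication and careful event definitions cannot recover it.

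**Working it through.** The protocol gives no figure on this point to reproduce. The check is a reading of the text in four steps, with date arithmetic for the look-back.

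**1. Does the rule reach endpoint events?** Section 14 defines an adverse event by reference to a study treatment, which suggests text carried over from a treatment trial. Its definition of a serious adverse event has no such tie: an undesirable medical event leading to hospitalization qualifies. An admission for infarction or unstable angina meets that. Sections 1 and 3 call the adjudicated endpoint events adverse events, and no section exempts them. Section 14 also says that the interview serves to gather adverse-event evidence across the whole case series. As worded, the rule applies.

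**2. Does the exception help?** It requires specific questions about resolution or continuation of events already reported. It does not provide for specific questions to discover a new event.

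**3. Do other sources make the interview redundant?** Sections 1, 3 and 8 list records, visits and telephone as alternatives, and the study-design row of the Synopsis names only telephone and outpatient visits. Records at this single centre should show events treated there. No section says that records are obtained from other hospitals. For an event treated elsewhere, the patient's answer may be the only lead.

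**4. How far back must patients recall?** Inputs: index procedures from January 2010 to December 2024 (Sections 1 and 10) and the protocol date of 1 March 2025 (Section 1). Assumption: first contact is no earlier than the protocol date. The gap g then runs from about 2 to 182 months (182/12 = 15.2 years). The distribution of index dates is not given, so two are assumed.

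| Assumed index dates | Mean gap | g > 12 months | g > 60 months |
|---|---|---|---|
| Evenly spread | (2 + 182)/2 = 92 months (7.7 years) | (182 − 12)/180 = 94% | (182 − 60)/180 = 68% |
| Rising linearly to 2024 | 2 + 180/3 = 62 months (5.2 years) | (170/180)² = 89% | (122/180)² = 46% |

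Under either assumption, most first contacts look back more than a year. This is elapsed time only. It does not measure missed events.

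**The case against.** The strongest reply is that Section 14 is safety text and was never meant to govern endpoint follow-up. Its language concerns study treatment, device malfunction and ministry incident forms. Sections 3, 7 and 8 deal with endpoints and follow-up and do not refer to Section 14. The Synopsis names the four adjudicated events, so follow-up has clear targets. Section 14 also says that a serious event after consent but before inclusion is not reported as one, which suggests that it looks forward from inclusion and not back to the index date.

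Much of this stands. The intent was probably safety reporting, and it is unclear whether the section governs the look-back at first contact. But the protocol never separates the two uses of the term. Even on the forward-looking reading, the rule still covers the later 12-monthly contacts.

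Other replies also carry some weight.

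- The rule says should, so staff may ask about infarction anyway. Good capture would then depend on staff departing from the text.
- An interview only points to an event, and documents establish it. That is correct, but without the pointer nobody requests an outside document.
- Non-leading questions are defensible when interviewers are not stated to be blind to FFR or treatment. Identical fixed questions for every patient meet that worry as well.
- Exact question wording belongs in the case report form or a call script. That is so, but such a script would now conflict with a stated protocol rule.

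A reader might go further and infer a definite loss of events, a fall in power or a biased hazard ratio. The documents do not support this. They give no capture rate and no share of events treated elsewhere. Section 11 states no effect size or comparison groups. Its event rates are for 12 months, whereas Section 12 analyses the whole follow-up. Cardiovascular death cannot be elicited from the patient. The same rule applies to everyone, and nothing in the text suggests that under-reporting would differ between groups.

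**Conclusion.** The point holds as a flaw in wording with a plausible but unproven effect. As written, the non-specific rule covers interviews used to find infarction, revascularization and admission for unstable angina, and nothing exempts those events. The exposure is confined to non-fatal events treated at other hospitals, for which the patient may be the only lead. Events treated at this centre should be recovered from its records.

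The number of missed events cannot be estimated from the documents, and no claim is made about power or hazard ratios. The look-back figures rest on the assumed first-contact date and the assumed spread of index dates. The conclusion does not depend on them. Priority is low to moderate.

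**What to change.** In Section 14, limit the non-specific rule to adverse events that are not endpoints. Then state that, at each planned contact, all patients are asked the same fixed questions:

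- any hospital admission for heart attack or unstable angina;
- any PCI or bypass surgery;
- in each case since the index procedure (first contact) or since the last contact (later contacts), with hospital and date.

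Add that the discharge letter is requested for the CEC whenever such an event is reported.

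The cost is one amended sentence, a short question list, slightly longer contacts and some work in requesting letters from other hospitals. No endpoint, definition, sample size or contact schedule changes.

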15. DEFINITIONS

Ischemia-driven target vessel revascularization (TVR)

All ischemia-driven revascularizations refer to the target lesion that led to enrollment into the study.

Requires the following criteria:

- Ischemic symptoms consistent with CCS class ≥ 3 angina despite optimal medical therapy

AND

- PCI or CABG of either the target that led to enrollment into the study PLUS at least ONE of the following:
 - Positive functional study (Exercise or myocardial perfusion imaging or stress or dobutamine echo) demonstrating clear evidence of reversible ischemia corresponding to a stenosis in the target vessel;
 - New ischemic ECG changes (ST-segment depression ≥ 1 mm, ST-segment elevation ≥ 1 mm or T wave inversion ≥ 2 mm) at rest or with exertion in a distribution consistent with a stenosis in the target vessel;
 - FFR ≤ 0.80 , iFR ≤ 0.89 , cFFR ≤ 0.85 , Angiography-derived FFR ≤ 0.80 in the target vessel.

Vessel-related myocardial infarction (MI)

MI is defined according to the 4th universal definition of myocardial infarction. The leading symptom that initiates the diagnostic and therapeutic cascade in patients with suspected MI is chest pain. Based on the electrocardiogram (ECG), two groups of patients should be differentiated: Patients with acute chest pain and persistent (>20 min) ST-segment elevation. This condition is termed ST-elevation ACS and generally reflects an acute total coronary occlusion. Most patients will ultimately develop an ST-elevation myocardial infarction (STEMI). The mainstay of treatment in these patients is immediate reperfusion by primary angioplasty or fibrinolytic therapy.

Patients with acute chest pain but no persistent ST-segment elevation. ECG changes may include transient ST-segment elevation, persistent or transient ST-segment depression, T-wave inversion, flat T waves or pseudo-normalization of T waves or the ECG may be normal. The clinical spectrum of NSTEMI may range from patients free of symptoms at presentation to individuals with ongoing ischemia, electrical or hemodynamic instability or cardiac arrest.

The pathological correlate at the myocardial level is cardiomyocyte necrosis. A small proportion of patients may present with ongoing myocardial ischemia, characterized by one or more of the following: recurrent or ongoing chest pain, marked ST depression on 12-lead ECG, heart failure and hemodynamic or electrical instability. Due to the amount of myocardium in jeopardy and the risk of malignant ventricular arrhythmias, immediate coronary angiography and, if appropriate, revascularization are indicated. The clinical definition of MI denotes the presence of acute myocardial injury detected by abnormal cardiac biomarkers in the setting of evidence of acute myocardial ischaemia.

Any MI without a clearly identifiable culprit vessel is counted as target vessel related.

Cardiovascular death

Deaths are classified as cardiovascular, non-cardiovascular, or of undetermined cause according to ARC-2 criteria. Deaths of undetermined cause are classified as cardiovascular but as a separate subcategory of cardiovascular deaths to indicate this uncertainty. Deaths due to procedural complications or concomitant treatments are classified as cardiovascular. Only deaths due to a documented non-cardiovascular cause (e.g., cancer) are classified as non-cardiovascular. Cardiovascular deaths in patients with multivessel disease are assigned to each affected vessel.

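### Section 15 ties the TVR component of a vessel-oriented primary endpoint to the target lesion, and its procedure criterion names neither lesion nor vessel

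*Protocol*

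**What the plan says.** The Synopsis (Section 1) describes a vessel-oriented composite, "including target vessel revascularization (TVR), target vessel-related myocardial infarction (MI), and cardiovascular death". Section 7 names the same three components and also puts the revascularization at target-vessel level.

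Section 15 holds the operational definition. Its heading is "Ischemia-driven target vessel revascularization (TVR". The scope sentence below it reads "All ischemia-driven revascularizations refer to the target lesion that led to enrollment into the study". The definition then requires angina of CCS class 3 or higher despite optimal medical therapy, together with "PCI or CABG of either the target that led to enrollment into the study PLUS at least ONE of the following". Three kinds of supporting evidence follow:

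- a functional study "demonstrating clear evidence of reversible ischemia corresponding to a stenosis in the target vessel";
- "New ischemic ECG changes" in a distribution that fits a stenosis in the target vessel;
- a physiology threshold from a list of indices that ends with "Angiography-derived FFR ≤ 0.80 in the target vessel".

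Section 3 places event definitions and adjudication rules in a committee charter, which is not at hand.

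**The concern.** TVR is one of three components of the primary endpoint and is also a secondary endpoint by itself. If one line of its definition counts any qualifying revascularization in the vessel and another counts only the index lesion, two adjudicators can each follow the protocol and classify the same event differently. The case is foreseeable. Section 10 plans follow-up to 10 years, and Section 12 bases the primary analysis on all events up to database lock, so there is ample time for another lesion in the same vessel to be treated.

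The second issue is smaller. Section 4 relates functional lesion characteristics to VOCE, so index FFR or angiography-derived FFR is the exposure. A physiology criterion without a date leaves open whether that same index value may later support the outcome.

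**Working it through.** No figure in the protocol bears on this point, so the check compares the texts.

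**Step 1: the level at which each line places the revascularization**

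| Place | Site named |
|---|---|
| Section 1, primary endpoint | target vessel |
| Section 7, primary endpoint | target vessel |
| Section 15, heading | target vessel |
| Section 15, scope sentence | target lesion |
| Section 15, procedure criterion | only a target; no noun, and *either* has no second alternative |

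The three ischaemia criteria also mention the target vessel, but they say where the evidence must lie, not which site was revascularized. Each is compatible with a target-lesion event, so they do not settle the level. The rule that "Any MI without a clearly identifiable culprit vessel is counted as target vessel related" concerns MI and does not define TVR.

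**Step 2: a test case for the level.** Lesion A in a vessel was assessed at the index procedure. Years later the patient has CCS class 3 angina despite optimal therapy, a stress test shows ischaemia matching a stenosis in that vessel, and PCI is done on lesion B in the same vessel.

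- Sections 1 and 7 and the Section 15 heading: event.
- Scope sentence: not an event, because it covers all ischaemia-driven revascularizations and points to lesion A.
- Procedure criterion: undetermined.

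The heading cannot overrule the scope sentence, because that sentence is worded to cover every case.

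**Step 3: a test case for the date.** Of the three ischaemia criteria, only the ECG criterion has a time word. Take two patients with the required angina and a later PCI of the index lesion, neither with a stress test, new ECG changes or physiology at the time of the event.

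| Index FFR | Undated literal reading | Event work-up reading |
|---|---|---|
| 0.80 or less | counts | does not count |
| above 0.80 | does not count | does not count |

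Only under the literal reading does the exposure decide whether the event counts. Even then it supplies one limb: the symptoms and an actual PCI or CABG are still needed.

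**Step 4: size.** A size would need the number of repeat revascularizations outside the index lesion, the share of index values at or below 0.80, and the share of repeat procedures without evidence from the time of the event. The protocol gives none of these. Section 11 quotes composite 12-month rates of 6.1% and 6.7% from other trials, not split by component, and does not say that those composites equal VOCE. No estimate follows from them.

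**The case against.** On the level, the best defence is that the lesion wording is a slip which any reader of a vessel-oriented endpoint would correct, and that the charter may already do so. That may be how it works in practice. It does not mend the protocol, whose Section 13 relies on predefined definitions and objective criteria to limit bias.

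On the date, the defence is stronger, and most of it stands:

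- The physiology criterion is attached to the event procedure, so the natural reading is evidence supporting that procedure.
- Section 3 gives the committee anonymized documents about the reported event and blinds it to clinical data. The index value is not expressly withheld, but it need not be in front of the adjudicators.
- Sections 6 and 8 say that index physiology guided the choice to treat or defer. A value measured before treatment no longer describes a vessel that was then treated.
- The list includes iFR and cFFR, which are not the index tests, and the functional-study criterion is undated too. Both suggest loose drafting, not intent.

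A reader might infer that the exposure is built into the outcome and that the association of FFR with VOCE is circular. The document does not support that. It permits the reading but does not prescribe it, index values above 0.80 cannot be used in this way, and the charter may rule it out.

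A reader might also count the ischaemia criteria as further votes for vessel level. They are not, for the reason given in step 1.

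**Conclusion.** The level conflict holds on the text alone, with high confidence. Sections 1 and 7 and the Section 15 heading define a vessel-level event, the scope sentence defines a lesion-level one, and the procedure criterion decides nothing. It changes which events enter a primary-endpoint component and should be corrected.

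The missing date on the physiology criterion is a true gap in wording but only a request for clarification. Whether it is open in practice depends on a charter that is not shown.

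Neither the size nor the direction of any bias can be derived from the protocol. Sections 1 and 7 also omit the ischaemia-driven qualifier that Section 15 carries. A reader might infer that they intend a different endpoint, but the document does not show this, and the point made here does not depend on it.

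**What to change.** Before adjudication:

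1. In the Section 15 scope sentence, replace *target lesion* with *target vessel*, and complete the procedure criterion as *PCI or CABG of the target vessel*. If lesion level is truly intended, change Sections 1 and 7 and the Section 15 heading instead.
2. Add one sentence to the physiology criterion: the qualifying measurement comes from the work-up of the repeat revascularization, and the index FFR or angiography-derived FFR does not qualify.
3. Align the adjudication charter with the corrected text.

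The change is to wording only. Its net effect on the TVR count is unknown: moving from lesion to vessel can raise it, and dating the physiology can lower it. The protocol does not say how often physiology from the time of the event can be found in records reaching back to 2010, so some repeat procedures may have to qualify through the functional-study or ECG criterion or not count.
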